#### Interim Analysis

The interim analysis will be performed when 29 patients have either (a) completed study treatment or (b) have reached the 6 month time point without being removed from study treatment, or when the combination of (a) and (b) reaches 29.

Patients remaining in the study at the time of the interim analysis will continue on treatment and will remain in the study, per the protocol.

Enrollment of new patients will be temporarily suspended after the first 29 evaluable patients (satisfying the above (a) and (b) criteria) are identified, in order to perform the primary interim analysis needed to determine whether to proceed to stage two, unless the data are such that reaching (or not reaching) the first-stage boundary is determinate.

#### **7.1.2 Secondary and exploratory analyses**

The overall response rate (CR + PR) will be calculated and reported, in addition to the median progression free survival and overall survival (OS) times for the study population. Median PFS and OS will be estimated along with 90% confidence intervals using the method of Brookmeyer and Crowley. Patients will be followed via phone calls and or medical records review even after coming off treatment for completion of the data for the PFS and OS endpoints. The PFS6, overall response rate, and OS will also be calculated among the predefined subset of patients with qualifying alterations exclusive of *EGFR* alterations.

Exploratory analysis of tumor tissue in all patients will be conducted for determination of whether specific alterations (including investigation/confirmation of any alterations by alternative methods), tumor EGFR and/or HER2 expression status (IHC), epithelial to mesenchymal transition states, novel microRNAs, and/or RNA or DNA profiling have bearing on PFS. This will also include consideration of tumor genomic alterations found during screening via CLIA laboratory testing. We will also examine the rate of liver metastases (at enrollment) in patients reaching the PFS6 endpoint, versus those who do not. Cox regression models will be fit to test for associations with PFS. Additional analyses based on logistic regression modelling will examine associations between variables and partial or complete response.

For the IHC testing secondary analysis, patients with EGFR IHC scores of 2+ and 3+ will be compared against patients with 0 or 1+ EGFR IHC scores for the primary endpoint (PFS). Similarly, patients with HER2 IHC scores of 2+ or 3+ will be compared to those with 0 or 1+ for the primary endpoint. Finally, patients with overexpression of *either* marker (defined as 2+ or 3+ IHC score for either EGFR or HER2) will be compared against those lacking

overexpression for both markers (EGFR and HER2 0 or 1+) for the primary endpoint. Prior exploratory studies have demonstrated this to be a potentially informative stratification.

Somatic alteration results generated from the CLIA laboratory reports used for screening in this study will also be compiled and stored indefinitely in a research study database at The University of Chicago for the purposes of future cancer research by the study investigators. This will include all patients who screen for the study regardless of whether they ultimately receive treatment with study drug.

### **7.1.3 Safety analyses**

Safety analyses can occur at any time deemed necessary by the lead investigator or the drug sponsor and must occur at the first interim analysis (29 patients) and at the end of the study. Adverse event rates will be summarized by type, grade, and attribution and descriptive statistics (frequency distributions) generated.

## **7.2 HANDLING OF MISSING DATA**

A modified intention to treat (ITT) analysis will be performed which will include all patients who begin treatment with the drug (i.e., at least 1 dose administered). Thus patients who withdraw from therapy due to adverse events or for any other reason prior to 6 months will be counted as failures with respect to the primary endpoint (PFS). Additional secondary analyses may be conducted excluding patients who discontinued treatment for reasons other than drug toxicity.

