# **7. STATISTICAL METHODS**

## **7.1 PLANNED ANALYSES**

### **7.1.1 Primary analyses**

This is a continuation of a single-arm phase II study. The previous phase of this study allowed enrollment of patients without respect to genomic marker status ('non-marker selected population'). That prior phase has been fully accrued (total n=23 patients), completed, and has been analyzed separately per the original statistical plan.

The present continuation portion of this phase II trial will enroll only patients whose tumors harbor genomic alterations in one or more of the *ErbB* family genes. This will comprise the 'marker-selected population' of this continuation trial.

In a meta-analysis of second-line clinical trials in patients with advanced urothelial carcinoma, the overall estimated progression-free survival (PFS) rate at 6 months was 22.6% (95% CI: 18.8%-25.9%), although it varied from 34.6% in patients with no risk factors (liver metastases, ECOG 1+, Hb<10 g/dl, or time from previous chemotherapy <6 months) to 4.9% in patients with 3-4 risk factors. Thus over three-quarters of patients will have disease progression within 6 months, and we propose that PFS at 6 months would be an informative endpoint for assessing drug activity.

For this continuation (marker-selected population) phase, a Simon, optimal two-stage design will be employed to assess the primary end point of 6-month PFS rate. The null hypothesis ( $H_0$ ), a 6-month PFS of <25%, will be considered representative of lack of efficacy of the drug in this biomarker-specific patient population consisting of patients with *ErbB* alterations. The alternative hypothesis ( $H_A$ ), a 6-month PFS rate of >40%, will be

considered indicative of activity. PFS will be defined as the time from enrollment until disease progression or death from any cause, and will be estimated using the Kaplan-Meier method, although we will follow the last patient entered for a minimum of 6 months to ensure that there is no censoring prior to 6 months. For determination of the PFS curve, patients who are alive and progression-free will be censored as of the date of the last negative evaluation.

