For 90% power at one-sided alpha = 0.10, n=72 patients will be needed. Assuming the frequency of having an alteration in any of the four genes is 20%, this will require screening approximately 360 patients. In the first stage, 29 patients will be enrolled and if 7 or fewer are alive and progression-free at 6 months the trial will be terminated for futility. Otherwise an additional 43 patients will be enrolled. At the end of the second stage, if 22 or fewer are alive and progression-free at 6 months the null hypothesis will be accepted and the treatment considered to be of insufficient efficacy, whereas if 23 or more (> 32%) exhibit progression-free survival of 6 months or more the regimen will be considered promising and worthy of further study.

Vinflunine is approved for use in urothelial cancer patients in the second-line setting in Europe. Separately, atezolizumab, nivolumab, durvalumab, and pembrolizumab have recently been FDA approved and/or studied in this setting as well and have shown significant activity despite not showing demonstrable changes in PFS. We therefore contend that our chosen 6-month observed PFS rate of 32% or higher required to consider afatinib promising would compare afatinib very favorably in this disease. This level of activity would warrant consideration of further testing of afatinib in this disease and biomarker subgroup.

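### Section 7.2 fails every withdrawal from therapy before 6 months for the primary endpoint, but the endpoint, PFS definition and boundary wording in 5.1.1 and 7.1.1 omit that rule, and the stated power does not allow for it

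*Combined protocol and SAP*

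**What the plan says.** Section 7.1.1 states that "PFS will be defined as the time from enrollment until disease progression or death from any cause". Stopping treatment is not an event. Both decision rules follow that definition: at stage 1, "if 7 or fewer are alive and progression-free at 6 months the trial will be terminated for futility"; at the end, "if 22 or fewer are alive and progression-free at 6 months the null hypothesis will be accepted". The design claim is "For 90% power at one-sided alpha = 0.10, n=72 patients will be needed", for 6-month PFS rates of 25% (null) and 40% (alternative). Section 5.1.1 names the primary endpoint simply as the 6-month PFS rate.

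Section 7.2 sets a modified intention-to-treat population (at least one dose) and then says that "patients who withdraw from therapy due to adverse events or for any other reason prior to 6 months will be counted as failures". The sentence goes on to tie this to the primary endpoint. It makes no exception for patients whose progression-free status at month 6 is known. It adds: "Additional secondary analyses may be conducted excluding patients who discontinued treatment for reasons other than drug toxicity".

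The Interim Analysis text counts a patient towards the 29 once treatment is complete, or once they "have reached the 6 month time point without being removed from study treatment".

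Section 7.1.2 continues follow-up for PFS and overall survival, by phone or record review, after treatment ends.

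**The concern.** Take a patient who stops drug at month 4 because of toxicity and is documented as progression-free at month 6. Section 7.1.1 counts a success and 7.2 counts a failure. The boundary text does not refer to 7.2, and 7.2 does not mention the boundaries.

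The stage 1 stop and the final verdict are the trial's only efficacy decision rules, and one patient separates 7 from 8 or 22 from 23. If the count is chosen once outcomes are known, the decision is open to challenge.

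If 7.2 governs, a second issue follows. The endpoint is then a composite that also fails treatment withdrawal, while the 25% and 40% rates are argued from PFS. The historical 6-month PFS of 22.6% cited in 7.1.1 may not be like for like with that composite.

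**Working it through.** **Inputs.** From 7.1.1: null 25%, alternative 40%, stop if 7 or fewer of 29, accept the null if 22 or fewer of 72 (43 more patients in stage 2), one-sided alpha 0.10, power 90%. Assumed, because the documents give no figure: w, the share of patients truly progression-free at 6 months who have stopped therapy by then.

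**Formulas.** With success probability p per patient:

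- P(stop at stage 1) = P(Bin(29, p) ≤ 7)
- P(reject null) = sum over x from 8 to 29 of P(Bin(29, p) = x) × P(Bin(43, p) ≥ 23 − x)

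**Step 1: reproduce the plan.** At p = 0.25, P(reject) = 9.77%. At p = 0.40, P(reject) = 90.11%, with a 5.70% chance of stopping at stage 1. The stated design is reproduced.

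**Step 2: apply the 7.2 count.** If true PFS at 6 months, as 7.1.1 defines it, is 40%, the success probability under 7.2 is 0.40 × (1 − w). Under the null it is 0.25 × (1 − w).

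| w (assumed) | p at 40% | Power | Stage 1 stop at 40% | p at 25% | Type I error |
|---|---|---|---|---|---|
| 0 | 0.400 | 90.1% | 5.7% | 0.2500 | 9.8% |
| 2% | 0.392 | 87.8% | 6.8% | 0.2450 | 8.2% |
| 5% | 0.380 | 83.7% | 8.6% | 0.2375 | 6.1% |
| 10% | 0.360 | 74.7% | 12.6% | 0.2250 | 3.6% |

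**Step 3: how often the choice of count changes the verdict.** Every success under 7.2 is also a success under 7.1.1. The chance of opposite final verdicts is therefore the power gap: 90.1 − 87.8 = 2.3 points at w = 2%, 90.1 − 83.7 = 6.4 at 5%, and 90.1 − 74.7 = 15.4 at 10%. The expected number of reclassified successes is 72 × 0.40 × w = 0.6, 1.4 and 2.9 patients.

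**Step 4: the alternative reading of 25% and 40%.** If these are rates of the 7.2 endpoint, power is 90.1% as stated. The target PFS rate as 7.1.1 defines it is then 0.40 / (1 − w) = 40.8%, 42.1% or 44.4% at w = 2%, 5% or 10%. The documents do not state this reading.

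**The case against.** The strongest reply is that the plan does answer the question. Section 7.2 ties its failure rule to the primary endpoint, and 7.1.1 says the two-stage design tests that endpoint. The interim readiness rule turns on treatment status. Analyses that exclude discontinued patients are placed among the secondary ones, which implies that the failure count is primary. The censoring sentence in 7.1.1 ("patients who are alive and progression-free will be censored as of the date of the last negative evaluation") is limited to the PFS curve, so it is not a rival success rule. Following the last patient for 6 months removes administrative censoring only. The section heading about missing data can hardly narrow a rule that covers withdrawal for any reason.

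This stands. A reader might infer that nothing in the plan indicates which count feeds the boundaries; the documents do not support that. What remains is that the endpoint, the PFS definition and the boundary wording omit the rule and, read alone, give the opposite answer for the same patient. Off-treatment follow-up for PFS keeps that answer available, although it may serve only median PFS and overall survival.

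The second reply is that the size is assumed and the direction conservative. That also stands. Section 3.3.4 lists several reasons to stop other than progression, so w above zero is possible. The one stop without progression described for the first portion (section 2.2) came at 10.3 months, after month 6, so it gives no rate. At w = 2% the loss is only 2.3 points.

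**Conclusion.** The point holds as a modest correction to wording and to the power statement. Section 7.2 is the better-supported rule for the 7/29 and 22/72 counts, but 5.1.1 and 7.1.1 do not carry it. If it governs, 90% power at a 40% PFS rate as defined in 7.1.1 requires w = 0. For assumed w of 2% to 10%, power is 87.8% to 74.7%, and the chance of a false futility stop at stage 1 rises from 5.7% to between 6.8% and 12.6%.

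A reader might infer that the conflict puts a favourable result in doubt. It does not: failing more patients can only lower type I error (9.8% at w = 0, 3.6% at w = 10%). Nor do the documents show that power has in fact been lost, since w is unknown and the stated 90% stands if 25% and 40% are meant as rates of the 7.2 endpoint.

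**What to change.** State in 5.1.1, 7.1.1, 7.2 and the Interim Analysis text which single count is compared with both boundaries, and report the other as a sensitivity analysis. The choice is the sponsor's.

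- **Option A, keep the 7.2 rule.** Define success in 7.1.1 as being alive, progression-free and not withdrawn from therapy at 6 months, and name the endpoint that way in 5.1.1. Either restate power over a range of w or declare that 25% and 40% are rates of this endpoint. Note that the historical comparator may not be like for like. The interim rule can stay. The downside is that power remains below 90% for a 40% PFS rate as now defined if w is above zero.
- **Option B, keep the 7.1.1 definition.** Limit 7.2 to patients whose 6-month progression status is unknown. Make the interim wait until each of the first 29 treated patients has progressed, died, or has a 6-month status that is known or declared unknown. Say how a patient who starts other anti-cancer therapy before month 6 is counted. There are three downsides. Scheduled scans end at drug intolerance (5.1.1, 6.1), so off-treatment status is less reliable and missed progressions would inflate the rate. The interim may wait up to 6 months from enrollment for early stoppers. Lost power is only partly recovered: if half of the early stoppers have unknown status (assumed), p = 0.40 × (1 − 0.5w), giving power of 87.2% at w = 5% and 83.7% at w = 10%.

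Either option costs wording and, where needed, a short power note. Neither adds patients.

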## **8. Informed Consent, Data Protection, Study records**

### **8.1 STUDY APPROVAL, PATIENT INFORMATION, AND INFORMED CONSENT**

This study will be initiated only after all required legal documentation has been reviewed and approved by the responsible Institutional Review Board IRB at each participating institution and the FDA according to national and international regulations. The same applies for the implementation of changes introduced by amendments.

In obtaining and documenting informed consent, the investigator should comply with the applicable regulatory requirement(s), and should adhere to Good Clinical Practice (GCP) and to ethical principles that have their origin in the Declaration of Helsinki.

Before recruitment and enrollment onto this study, the patient will be given a full explanation of the study and will be given the opportunity to review the consent form. Each consent form must include all the relevant elements currently required by the FDA Regulations and local or state regulations. Once this essential information has been provided to the patient and the investigator is assured that the patient understands the implications of participating in the study, the patient will be asked to give consent to participate in the study by signing an IRB approved consent form.

Each signature must be personally dated by each signatory and the informed consent and any additional patient-information form retained by the investigator as part of the study records.

A signed copy of the informed consent and any additional patient information must be given to each patient or the patient's legally accepted representative. The patient must be informed that his/her personal study-related data will be used by the Principal Investigator in accordance with the local data protection law. The level of disclosure must also be explained to the patient.

The patient must be informed that his / her medical records may be examined by authorized monitors (CRA) or Clinical Quality Assurance auditors appointed by the Principal Investigator, by appropriate IRB members, and by inspectors from regulatory authorities.

## **Required Documentation**

Before the study can be initiated at any site, the following documentation must be provided to the Cancer Clinical Trials Office (CCTO) at the University of Chicago Comprehensive Cancer Center.

- A copy of the official IRB approval letter for the protocol and informed consent
- IRB membership list
- CVs and medical licensure for the principal investigator and any sub-investigators who will be involved in the study
- Form FDA 1572 appropriately filled out and signed with appropriate documentation (a copy of the completed form may be sent to the CCTO and the original should be retained in the site regulatory files)
- CAP and CLIA Laboratory certification numbers and institution lab normal values
- Investigational drug accountability standard operating procedures
- Additionally, before the study can be initiated at any site, the required executed research contract/subcontract must be on file with the University of Chicago.

## **Data and Safety Monitoring**

This study will be remotely monitored by the designated University of Chicago Clinical Research Associate (CRA) in accordance with University of Chicago, Section of Hematology/Oncology standard operating procedures.

Prior to subject recruitment, and unless otherwise specified, a participating site will undergo site initiation teleconference to be conducted by the designated University of Chicago research team. The site's principal investigator and his or her study staff must attend the site initiation meeting.

Monitoring will be conducted to verify the following:

- Adherence to the protocol
- Completeness and accuracy of study data and samples collected
- Compliance with regulations

Participating sites will also undergo a site close-out teleconference upon completion, termination or cancellation of a study to ensure fulfillment of study obligations during the

conduct of the study, and to ensure that the site Investigator is aware of his/her ongoing responsibilities.

Unless otherwise specified, this protocol will undergo weekly review at the multi-institutional data and safety monitoring teleconference as per procedures specified by the UC CCC NCI-approved Data and Safety Monitoring Plan. The conference will review:

- Enrollment rate relative to expectations, characteristics of participants
- Safety of study participants (Serious Adverse Event & Adverse Event reporting)
- Adherence to protocol (protocol deviations)
- Completeness, validity and integrity of study data
- Retention of study participants

Protocol deviations are to be documented using the Protocol Deviation Form and sent via email to [[contact]](mailto:[contact]). Deviations that are considered major because they impact subject safety or alter the risk/benefit ratio, compromise the integrity of the study data, and/or affect subjects' willingness to participate in the study must be reported within 7 days. Please contact the University of Chicago CRA ([[contact]](mailto:[contact])) if you have questions about how to report deviations. All major protocol deviations should also be reported to the local IRB of record according to their policies and procedures.

## **8.2 DATA QUALITY ASSURANCE**

In addition to the clinical monitoring procedures, the University of Chicago Cancer Clinical Trials Office (CCTO) will perform routine Quality Assurance Audits of investigator-initiated clinical trials as described in the NCI-approved UCCCC DSM Plan. Audits provide assurance that trials are conducted and study data are collected, documented and reported in compliance with the protocol. Further, they ensure that study data are collected, documented and reported in compliance with Good Clinical Practices (GCP) Guidelines and regulatory requirements by performing annual quality assurance audits. The CCTO will review subjects enrolled at the University of Chicago in accordance with audit procedures specified in the UCCCC Data and Safety Monitoring plan.

For institutions who are formal members of the PCCC, the University of Chicago Comprehensive Cancer Center (UCCCC) will conduct on site quality assurance audits on average every two years during the enrollment and treatment phase of the study.

Auditing procedures for participating sites that are not full members of the PCCC must be specified and approved by the UCCCC Clinical Research Advisory Committee. In general, for sites that are not full members of the PCCC, auditing responsibility will be delegated to the participating center, with the annual audit report forwarded to the University of Chicago for review.

A regulatory authority (e.g. FDA) may also wish to conduct an inspection of the study, during its conduct or even after its completion. If an inspection has been requested by a regulatory

authority, the site investigator must immediately inform the University of Chicago Cancer Clinical Trials Office and Regulatory Manager that such a request has been made.

## **Amendments to the Protocol**

All modifications to the protocol, consent form, and/or questionnaires will be submitted to the University of Chicago IRB for review and approval. A list of the proposed modifications or amendments to the protocol and an explanation of the need of these modifications will be submitted, along with a revised protocol incorporating the modifications. Once a protocol amendment has been approved by the University of Chicago IRB, the Regulatory Manager will send the amended protocol and consent form to the affiliate institutions electronically. Upon receipt of the packet the affiliate institution is expected to do the following:

- The affiliate must reply to the email from the Regulatory Manager indicating that the amendment was received by the institution and that it will be submitted to the local IRB.
- The amendment should be submitted to the affiliate institution's IRB as soon as possible after receipt. The amendment must be IRB approved by the institution within 3 months from the date that it was received.
- The University of Chicago version date and/or amendment number must appear on the affiliate consent form and on the affiliate IRB approval letter. The version dates can be found on the footer of every page of the protocol and consent form. The amendment number can be found on the University of Chicago IRB amendment approval letter that is sent with the protocol/amendment mailing.
- The IRB approval for the amendment and the amended consent form (if amended consent is necessary) for the affiliate institution must be sent to the designated UC Regulatory Manager as soon as it is received.

